## Secondary Outcomes

Secondary outcomes will include additional clinical outcomes, additional renal outcomes, and biochemical outcomes. Additional clinical outcomes will include in-hospital mortality before ICU discharge, before 30 days, and before 60 days; ICU-free days, ventilator-free days, vasopressor-free days, and RRT-free days, all through 28 days after enrollment. Additional renal outcomes will include new RRT receipt, persistent renal dysfunction, stage II or greater AKI by Kidney Disease Improving Global Outcomes (KDIGO) creatinine criteria[26], highest serum creatinine value, change from

baseline creatinine to highest creatinine, final serum creatinine value before hospital discharge, and duration of new RRT. Biochemical outcomes will include serum values for sodium, potassium, chloride, bicarbonate, blood urea nitrogen, and creatinine from enrollment through day 30.

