## Population

All adults (age  $\geq 18$  years) admitted to a participating ICU at Vanderbilt University Medical Center during the study period are enrolled at the time of ICU admission. Enrolled patients who are discharged from the hospital are eligible again if they are admitted to a participating ICU again during the study period.

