## Primary Outcome

The primary outcome will be the proportion of patients meeting one or more criteria for Major Adverse Kidney Events within the 30 days after enrollment (MAKE30): in-hospital mortality, receipt of new RRT, or persistent renal dysfunction defined as a final inpatient serum creatinine value  $\geq 200\%$  of baseline[22–24]. In-hospital mortality will be defined as death from any cause prior to hospital discharge censored at 30 days after ICU admission. Receipt of new RRT will be defined as receipt of any modality of RRT between ICU admission and the first of hospital discharge or 30 days, among patients not known to have received RRT prior to ICU admission. Persistent renal dysfunction will be defined as a final serum creatinine value before hospital discharge (censored at 30 days after enrollment)  $\geq 200\%$  of the baseline creatinine value. The value for baseline serum creatinine will be determined using a previously-described hierarchical approach[22]. The lowest serum creatinine between 12 months and 24 h prior to hospital admission will be used when available. If no such creatinine value is available, the lowest creatinine value between 24 h prior to hospital admission and the time of ICU admission will be used. If no creatinine value is available between 12 months prior to hospital admission and the time of ICU admission, a baseline creatinine value will be estimated using a previously-described formula [creatinine =  $0.74 - 0.2$  (if female) +  $0.08$  (if African American) +  $0.003 \times$  age (in years)][25]. Patients known to have received RRT prior to enrollment will be considered ineligible to meet criteria for new RRT or persistent renal dysfunction, but may qualify for MAKE30 by experiencing in-hospital mortality.

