### **Statistical Analysis Principles**

All analyses will be performed using R version 3.2.0 (R Foundation for Statistical Computing, Vienna, Austria). To maximize transparency and reproducibility, a complete version of the R code that will be used to analyze the final study data is available in Additional File 1. This ensures that (1) statistical reviewers or external investigators will be able to replicate the pre-specified analysis of the trial independently and (2) any changes or additions to the statistical analysis introduced by investigators or reviewers after completion of enrollment will be evident as differences between the pre-specified code and the analysis code included with the final publication.

All analyses will be conducted at the level of the individual patient during an individual hospitalization in an intention-to-treat fashion unless otherwise specified. Continuous variables will be reported as mean  $\pm$  standard deviation, mean and 95% confidence interval, or median and interquartile range; categorical variables as frequencies and proportions. Between-group comparisons will be made with the Mann-Whitney rank sum test for continuous variables, chi-square test for categorical variables, generalized estimating equations for repeatedly measured variables, and generalized linear mixed-effects models for analyses of the primary and secondary outcomes. A two-sided  $P$  value  $< 0.05$  will be considered to be statistically significant.

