**Table 2. Clinical Outcomes.**

Outcome	Saline (n =)	Balanced (n =)	Adjusted OR (95% CI)	Adjusted P Value
Primary Outcome				
Major Adverse Kidney Event within 30 days, No. (%)	--	--	--	--
Secondary Clinical Outcomes				
In-hospital mortality, No. (%)				
Before ICU discharge	--	--	--	--
Before 30 days	--	--	--	--
Before 60 days	--	--	--	--
ICU-free days, median [IQR]	--	--	--	--
Mean ± SD	--	--		
Ventilator-free days, median [IQR]	--	--	--	--
Mean ± SD	--	--		
Vasopressor-free days, median [IQR]	--	--	--	--
Mean ± SD	--	--		
Renal replacement therapy-free days, median [IQR]	--	--	--	--
Mean ± SD	--	--		
Secondary Renal Outcomes				
Serum creatinine, mg/dL				
Highest before discharge or day 30, median [IQR], mg/dL	--	--	--	--
Change from baseline to highest value, median [IQR], mg/dL	--	--	--	--
Final value before discharge or 30 days, median [IQR], mg/dL	--	--	--	--
Among survivors, median [IQR], mg/dL	--	--	--	--
Final creatinine > 200% baseline, No. (%)	--	--	--	--
Among survivors to hospital discharge	--	--	--	--
Among survivors to hospital discharge without new RRT	--	--	--	--
Acute kidney injury, stage II or greater, No. (%)	--	--	--	--
Developing after enrollment	--	--	--	--
Receipt of new renal replacement therapy, No. (%)	--	--	--	--
Duration of in-hospital receipt, median [IQR], days	--	--	--	--
Continued receipt after hospital discharge, No. (%)	--	--	--	--

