### **Outcomes**

**Major Adverse Kidney Events within 30 days (MAKE30).** The MAKE30 composite outcome will be considered to have occurred when patients meet one or more of the following criteria in the 30 days after enrollment: (1) in-hospital mortality, (2) receipt of new renal replacement therapy (RRT), or (3) persistent renal dysfunction. Patients who

have received RRT prior to enrollment will be ineligible to meet the new RRT or persistent renal dysfunction criteria but will remain eligible to meet criteria for in-hospital mortality.

**In-hospital mortality** – In-hospital mortality will be defined as death from any cause prior to hospital discharge censored at 30 days after ICU admission (30-day in-hospital mortality).

**Receipt of new renal replacement therapy** – Receipt of new RRT will be defined as receipt of any modality of RRT between ICU admission and the first of (1) hospital discharge or (2) 30 days in a patient not known to have received RRT prior to ICU admission.

**Persistent renal dysfunction** – Persistent renal dysfunction will be defined as a final serum creatinine value before hospital discharge (censored at 30 days after enrollment) that is  $\geq$  200% of the baseline creatinine value.

**ICU-free days** – Intensive care unit-free days to day 28 (ICU-free days) will be defined as the number of days from the time of the patient's physical transfer out of the ICU until day 28 after enrollment. Patients who die prior to day 28 after enrollment will receive a value of 0 for ICU-free days. Patients who are never transferred out of the ICU prior to day 28 after enrollment will receive a value of 0 for ICU-free days. Patients who are transferred out of the ICU, return to the ICU, and are not subsequently transferred out of the ICU again before day 28 after enrollment will receive a value of 0 for ICU-free days. For patients who are transferred out of the ICU, are readmitted to the ICU, and are subsequently transferred out of the ICU again prior to day 28 after enrollment, ICU-free days will be awarded based on the time of the final transfer out of the ICU prior to day 28 after enrollment.

**Ventilator-free days** – Ventilator-free days to day 28 (VFDs) will be defined as the

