For patients who achieve RRT cessation, return to receiving RRT, and subsequently achieve cessation of RRT again prior to day 28 after enrollment, RRT-free days will be awarded based on the time of the final RRT treatment prior to day 28 after enrollment. Survivors who never receive RRT will receive 28 RRT-free days.

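### The three continuous creatinine outcomes include patients dialysed before enrollment, which blurs what those rows measure and costs some precision

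*Combined protocol and SAP*

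**What the plan says.** - **Who is enrolled.** SAP, Population: all adults "admitted to a participating ICU at Vanderbilt University Medical Center during the study period are enrolled at the time of ICU admission". Earlier dialysis is not an exclusion.
- **Default analysis set.** SAP, Statistical Analysis Principles: "All analyses will be conducted at the level of the individual patient during an individual hospitalization in an intention-to-treat fashion unless otherwise specified".
- **The rule for earlier RRT.** SAP, Primary Outcome: "Patients known to have received RRT prior to enrollment will be considered ineligible to meet criteria for new RRT or persistent renal dysfunction". Appendix 2 repeats this under MAKE30. They can still meet MAKE30 by dying.
- **The creatinine outcomes.** SAP, Secondary Outcomes, names highest creatinine, then change from "baseline creatinine to highest creatinine, final serum creatinine value before hospital discharge, and duration of new RRT". Section 8.5 of the final protocol lists the same three creatinine outcomes. Neither place restricts them.
- **Reporting.** Table 2 has a row "Change from baseline to highest value, median [IQR], mg/dL", with similar rows for the highest and final values. It adds rows for survivors and for survivors without new RRT, but none that removes patients with earlier RRT. Its effect column is an adjusted odds ratio.
- **Method.** Statistical Analysis Principles names the Mann-Whitney test for continuous variables and, in the same sentence, "generalized linear mixed-effects models for analyses of the primary and secondary outcomes".

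**The concern.** The plan recognises that patients with earlier RRT cannot tell us about new RRT or persistent dysfunction. It then lets the same patients' creatinine values into three neighbouring outcomes.

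Baseline creatinine is, where available, the lowest value from the year before admission. The highest value is the maximum up to discharge or day 30. In someone on maintenance dialysis, whose creatinine falls with each session and climbs between sessions, the gap between that minimum and that maximum largely reflects session timing. (This is a clinical premise, not something the documents state.) The choice of fluid has little room to move it.

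Two things are at stake. One is interpretation: the rows describe a mixture of kidney injury and chronic dialysis. The other is precision: patients with large, uninformative values widen the spread and dilute any difference among patients at risk.

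**Working it through.** **1. The plan's own figure.** The SAP gives no power or standard deviation for these outcomes. Its power figure concerns MAKE30: 14,000 patients, a rate around 15%, a difference of 1.9 points, 90% power. With 7,000 per group, two-sided 0.05, pooled variance and no clustering, 15.0% v 13.1% gives 89.9%, and 15.95% v 14.05% gives 88.3%. The figure reproduces and does not depend on this point.

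**2. Inputs.** From the documents: enrollment of all adults, the intention-to-treat default, the rule limited to two criteria, and N = 14,000. Everything else is assumed:
- share with earlier RRT, q = 3% to 8%;
- change to highest creatinine without earlier RRT: mean m0 = 0.35 mg/dL, SD s0 = 0.8 or 1.2 mg/dL;
- change with earlier RRT: SD s1 and mean m1 of 2.0 and 2.5 mg/dL, or 3.0 and 4.0 mg/dL.

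**3. If means are modelled.**

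V = (1−q)·s0² + q·s1² + q(1−q)·(m1−m0)²

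Share of V due to earlier RRT = 1 − (1−q)·s0²/V

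Standard error, all patients relative to restricted = √[V(1−q)/s0²]

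| q | s0 | s1, m1 | V | Share | SE ratio |
|---|---|---|---|---|---|
| 3% | 0.8 | 2.0, 2.5 | 0.621 + 0.120 + 0.134 = 0.875 | 29% | 1.15 |
| 8% | 0.8 | 3.0, 4.0 | 0.589 + 0.720 + 0.980 = 2.289 | 74% | 1.81 |
| 3% | 1.2 | 2.0, 2.5 | 1.397 + 0.120 + 0.134 = 1.651 | 15% | 1.05 |
| 8% | 1.2 | 3.0, 4.0 | 1.325 + 0.720 + 0.980 = 3.025 | 56% | 1.39 |

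The range is therefore about 1.05 to 1.8. If the fluid does not move creatinine in patients with earlier RRT, the expected difference also shrinks by the factor 1−q (0.97 to 0.92).

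**4. If ranks are compared.** Assume highest creatinine is log-normal with median 1.1 mg/dL and log-SD 0.6 without earlier RRT, that balanced fluid lowers it by 4% (0.04 on the log scale), and that it has no effect in patients with earlier RRT. Then

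θ = Φ(0.04/(0.6·√2)) = 0.5188

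Power ≈ Φ(|θ−0.5|/√(2/(12n)) − 1.96), with n = 7,000 per group for all patients and n(1−q) when restricted.

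If the values of the two kinds of patient do not overlap, mixing them gives θ_all − 0.5 = (1−q)²(θ − 0.5). With overlap (earlier RRT: median 4.5 mg/dL, log-SD 0.5), θ_all is 0.5178 at 3% and 0.5162 at 8%.

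| q | Restricted | All, with overlap | All, no overlap | Loss (points) |
|---|---|---|---|---|
| 3% | 96.7% | 95.4% | 95.2% | 1.2 to 1.5 |
| 8% | 95.9% | 91.3% | 90.3% | 4.6 to 5.5 |

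These calculations ignore clustering throughout.

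**The case against.** **The large figures price an analysis the plan may not run.** This stands. Table 2 reports these outcomes as medians with an adjusted odds ratio, which points to an ordinal type of model, and the Mann-Whitney test is named. A reader might infer that dialysis patients would supply 29% to 74% of the variability. That holds only for a difference in means with an assumed SD of 0.8 mg/dL in the remaining patients; at 1.2 the share is 15% to 56%. The rank-scale loss is modest.

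**Inclusion is inferred from silence.** Partly stands. The SAP points to R code in an additional file that is not among these documents and could contain a filter. If it does, the text should say so.

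**The existing rule does not define an analysis population.** This stands. Appendix 2 says patients who "have received RRT prior to enrollment will be ineligible to meet the new RRT or persistent renal dysfunction criteria". They cannot be events on those criteria, but nothing removes them from the denominator. The restriction would create a new analysis set.

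**The filter is broader than maintenance dialysis.** Partly stands. Any earlier RRT could include patients no longer on dialysis, and the subgroup list has a separate category for end-stage disease on RRT. The broader flag does match the plan's own eligibility rule, and all-patient rows would show whether it matters.

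**The stakes are low.** This stands. Earlier RRT is a baseline factor expected to be similar in both groups, and the SAP labels secondary comparisons hypothesis-generating.

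**A reader might extend the point to RRT-free days.** Appendix 2 scores them with no separate rule for chronic dialysis: "RRT-free days will be awarded based on the time of the final RRT treatment". The extension is not supported. The SAP lists them among clinical rather than renal outcomes, and death before day 28 scores 0, so the filter would discard deaths that the plan deliberately counts for these patients. Nor is there a clear precision gain. In a simulation assuming 10% deaths and 2.5% new RRT, the standard error ratio is 0.97 to 0.99 if days are credited from the last in-hospital session, and 1.08 to 1.18 if continuing dialysis is scored 0.

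**Conclusion.** The point holds for highest, change-to-highest and final creatinine. As written, these cover all enrolled patients, including those with RRT before enrollment, although the SAP already treats those patients as unable to show persistent dysfunction or new RRT. The cost is a blurred meaning and some lost precision.

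The size cannot be derived from the documents. It rests on the assumed 3% to 8% share and the assumed creatinine distributions; the larger losses need both a mean-scale model and a small SD among patients at risk. Whichever test is used, the rows remain a mixture.

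Nothing here supports a claim of bias or any doubt about MAKE30. Cheap improvement.

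**What to change.** In the SAP's Secondary Outcomes section, and in a footnote to Table 2, state that highest creatinine, change from baseline to highest, and final creatinine are compared among patients not known to have received RRT before enrollment. Define the set by the earlier-RRT variable already collected at enrollment and tabulated in Table 1. Because it is a baseline variable, the restriction keeps the randomized comparison, which the survivor rows do not. Put the all-patient versions of the three rows in the supplement. Leave RRT-free days in the full population.

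The cost is one sentence, one footnote and one filter in the code. The downside is that denominators will differ between Table 2 rows, so each should be printed.

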## **8.4 Data Collection**

### **8.4.1 Data at Enrollment**

1. Study Enrollment Data:
  - a. Encounter Number ("Study ID")
  - b. Medical Record Number
  - c. Date and Time of ICU Admission ("Time Zero")
  - d. Study ICU at enrollment (Medical/Cardiac/Neuro/Trauma/Surgical)

Principal Investigators: [name], [name]

Version Date: 6/15/17

Study Title: Isotonic Solutions and Major Adverse Renal Events Trial (SMART)

Institution/Hospital: Vanderbilt University Medical Center

2. Demographic Data:

- a. Age (years)
- b. Gender (male/female)
- c. Race (White/Black/Asian/Alaskan/PacificIsland/Other)
- d. Ethnicity (Hispanic, Non-hispanic)
- e. Height (cm)
- f. Weight (kg)
- g. Date and time of Hospital Admission
- h. Source of admission to ICU (ED/OR/outside hospital transfer/hospital ward/outpatient/another ICU within the hospital)
- i. Admitting service
- j. ICD-9 and ICD-10 diagnoses

3. Comorbidities:

- a. Exlihauser comorbidities
- b. CKD stage III or greater by CKD-EPI criteria
- c. Prior receipt of renal replacement therapy
- d. Predicted risk of in-hospital mortality by University HealthSystem Consortium expected in-hospital mortality

4. Invasive Support:

The following information will be recorded during the 12 hours prior to and 24 hours following ICU admission (“Time Zero”). If more than one value is available for this 36-hour period, the value closest to the time of ICU admission (“Time Zero”) will be recorded.

- a. Receipt of Mechanical Ventilation (Y/N)
- b. Receipt of vasopressors (Y/N) (norepinephrine, epinephrine, dopamine, phenylephrine, or vasopressin)

5. Renal function

- a. All serum creatinine values from the clinical laboratory system between 12 months prior to hospitalization and 30 days after ICU admission
- b. Stage II or greater acute kidney injury by KDIGO creatinine criteria

6. Serum laboratory values

- a. All serum values for sodium, potassium, chloride, bicarbonate, and blood urea nitrogen between 12 months prior to hospitalization and 30 days after ICU admission

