### **Final Data Analysis Plan**

*(Published with Statistical Analysis Plan 3/16/17)*

All analyses will be performed using R version 3.2.0 (R Foundation for Statistical Computing, Vienna, Austria). All analyses will be conducted at the level of the individual patient during an individual hospitalization in an intention-to-treat fashion unless otherwise specified. Continuous variables will be reported as mean  $\pm$  standard deviation, mean and 95% confidence interval, or median and interquartile range; categorical variables as frequencies and proportions. Between-group comparisons will be made with the Mann-Whitney rank sum test for continuous variables, chi-square test for categorical variables, generalized estimating equations for repeatedly measured variables, and generalized linear mixed-effects models for analyses of the primary and secondary outcomes. A two-sided P value  $< 0.05$  will be considered to be statistically significant. As a large, pragmatic trial enrolling every adult admitted to the five participating intensive care units, the SMART study population will contain a wide spectrum of (1) exposure to the study intervention, (2) baseline risk of the primary outcome, and (3) physiologically-distinct patient subgroups. The primary and secondary analyses evaluate the effect of the intervention overall and across the spectrum of exposure to crystalloid, baseline risk of MAKE30, and patient subgroups.

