### Power Calculation

Based on data from the study ICUs in the year prior to the trial, we anticipate the planned study duration (Figure 1) will result in enrollment of around 14,000 patients with an overall rate of MAKE30 around 15%. Enrollment of 14,000 patients will provide 90% power at an alpha level of 0.05 to detect an absolute difference between the saline and balanced crystalloid groups in MAKE30 of 1.9%, a relative risk reduction of 12%, which is comparable to the 12% relative risk reduction for in-hospital mortality reported in a recent pilot trial[13] (additional details in the Appendix 3).

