**Table E4. Serum laboratory values.**

Laboratory value	Saline (n = )	Balanced (n = )	P value
Serum sodium, mmol/L			
Highest between enrollment and day 30, median [IQR]	--	--	--
Lowest between enrollment and day 30, median [IQR]	--	--	--
>145 between enrollment and day 30, No. (%)	--	--	--
< 135 between enrollment and day 30, No. (%)	--	--	--
Serum potassium, mmol/L			
Highest between enrollment and day 30, median [IQR]	--	--	--
Lowest between enrollment and day 30, median [IQR]	--	--	--
> 5.0 between enrollment and day 30, No. (%)	--	--	--
< 3.0 between enrollment and day 30, No. (%)	--	--	--
Serum chloride, mmol/L			
Highest between enrollment and day 30, median [IQR]	--	--	--
Lowest between enrollment and day 30, median [IQR]	--	--	--
> 110 between enrollment and day 30, No. (%)	--	--	--
< 90 between enrollment and day 30, No. (%)	--	--	--
Serum bicarbonate, mmol/L			
Highest between enrollment and day 30, median [IQR]	--	--	--
Lowest between enrollment and day 30, median [IQR]	--	--	--
> 30 between enrollment and day 30, No. (%)	--	--	--
< 20 between enrollment and day 30, No. (%)	--	--	--

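### The SAP text states no adjustment for the patient's own pre-enrollment value in the electrolyte, BUN and raw creatinine comparisons: a modest, avoidable loss of precision

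*Combined protocol and SAP*

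**What the plan says.** **Outcomes.** SAP, Secondary Outcomes: "Biochemical outcomes will include serum values for sodium, potassium, chloride, bicarbonate, blood urea nitrogen, and creatinine from enrollment through day 30". The same section lists highest creatinine, change from baseline to highest, and final creatinine among the renal outcomes.

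**Data.** Protocol (version 6/15/17), 8.4.1 Data at Enrollment, item 6: "All serum values for sodium, potassium, chloride, bicarbonate, and blood urea nitrogen between 12 months prior to hospitalization and 30 days after ICU admission". Item 5 of that section extracts creatinine over the same window.

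**Methods.** SAP, Statistical Analysis Principles, names the rank-sum test for continuous variables, chi-square for categorical ones, GEE for repeated measurements, and mixed-effects models for the primary and secondary outcomes. The only covariate list is in Primary Analysis: age, gender, race, source of admission, ventilation, vasopressors, sepsis and traumatic brain injury. It holds no laboratory value, and no covariates are stated for the GEE.

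**Tables.** Table E4 gives post-enrollment highest and lowest values and threshold counts for sodium, potassium, chloride and bicarbonate, with one plain P value column. Table 2 has adjusted columns and one continuous row that uses baseline: "Change from baseline to highest value, median [IQR], mg/dL". Table 1 shows baseline creatinine but no baseline electrolytes or BUN.

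**The concern.** A patient's earlier value of an analyte is usually a strong predictor of the later one. Leaving it out of the comparison keeps variance in the error term that could be removed at almost no cost, because the values are already extracted.

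The second issue is presenting values. The Table E4 window opens at enrollment, so a patient who arrives with low bicarbonate or high potassium can be counted before ICU study fluid has acted. The SAP separates prevalent from incident AKI (Appendix 2) but makes no such distinction for electrolytes. With no baseline electrolyte rows in Table 1, a reader could not see whether the groups arrived alike.

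These outcomes bear on mechanism (chloride, bicarbonate), on potassium safety and on part of the renal picture. The primary MAKE30 analysis is not involved.

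**Working it through.** **The plan's own figure.** SAP, Power Calculation: "Enrollment of 14,000 patients will provide 90% power at an alpha level of 0.05", for a 1.9-point difference with MAKE30 around 15%. Taking 15.0% against 13.1% with 7,000 per group (roughly equal months in each group):

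- SE = √[(0.15×0.85 + 0.131×0.869)/7000] = 0.00587
- 0.019/0.00587 = 3.24; 3.24 − 1.96 = 1.28; power = 0.899

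The stated 90% reproduces. The documents give no power for any biochemical outcome, so the rest is an illustration.

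**Inputs.** From the documents: 7,000 per group and two-sided 0.05. Assumed, because the documents do not give them: ρ, the correlation of pre- with post-enrollment value; equal SDs at both times; one complete summary per patient; no clustering; no other covariates.

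**Detectable difference at 90% power, in SD units.**

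- No baseline term: (1.960 + 1.282) × √(2/7000) = 3.242 × 0.0169 = 0.0548
- Baseline covariate: 0.0548 × √(1 − ρ²)
- Change score: 0.0548 × √[2(1 − ρ)]

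| ρ | Variance removed by covariate (ρ²) | Covariate | Change score |
|---|---|---|---|
| 0.3 | 9% | 0.052 | 0.065 |
| 0.5 | 25% | 0.047 | 0.055 |
| 0.7 | 49% | 0.039 | 0.042 |

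Below ρ = 0.5 the change score is less precise than the raw value. The covariate is never worse than either in large samples.

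**In units.** For an assumed electrolyte SD of 4 to 8 mmol/L, the unadjusted figure is 0.22 to 0.44 mmol/L. Adjusted, it is 0.19 to 0.38 at ρ = 0.5 and 0.16 to 0.31 at ρ = 0.7.

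**Power.**

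- Effect of 0.05 SD: 84% unadjusted, 93% at ρ = 0.5, 99% at ρ = 0.7.
- Effect of 0.10 SD: above 99.9% with or without baseline.
- Log creatinine, assumed SD 0.55, 2% difference (0.02/0.55 = 0.036 SD): SE = 0.55 × 0.0169 = 0.0093. Power is 58% unadjusted; over ρ = 0.5 to 0.7 it is 58% to 79% with the change score and 70% to 85% with the covariate. Unadjusted power is already about 90% for a 3% difference and 99% for 4%.

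**Sensitivity.** At the 15,000 and 16,500 patients now expected (protocol, Final Anticipated Sample Size), the unadjusted figure is 0.0529 and 0.0505 SD. With an assumed design effect of 2 or 4 on 14,000, it is 0.078 or 0.110 SD.

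**Chance imbalance.** Ignoring clustering, the difference in mean presenting value has SE √(2/7000) = 0.017 SD. Multiplied by ρ of 0.5 to 0.7, it carries 0.008 to 0.012 SD into the outcome.

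**The case against.** **Creatinine is largely covered.** A reader might infer that all creatinine outcomes ignore baseline. The documents do not support that. Change to highest is a listed outcome; persistent renal dysfunction is defined against the patient's own baseline, and stage II or greater AKI is largely so. Missing baseline creatinine has a rule and five sensitivity analyses (Appendix 5). The point is limited to highest, final and serial creatinine. This stands.

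**The sample is large.** A reader might also infer that between-patient variation would drown modest fluid effects. It would not: 0.055 SD is detectable unadjusted. This stands, with the qualification that the figure ignores clustering.

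**The gain is an upper range.** It compares with a covariate-free analysis. If the mixed models use the listed covariates, part of the variance is already explained. Formula-estimated baselines come only from sex, race and age, so for those patients (120 of 974, 12.3%, had no prior creatinine in the pilot) little is added. Both remarks stand for the mixed models; they do not help a rank-sum test.

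**Imbalance should be small.** The SAP Discussion relies on frequent crossovers, and the calculation above gives a small carry-through. But that calculation treats patients as individually randomized, whereas one randomization set the sequences for all five ICUs en bloc. The documents do not allow the bias to be sized, and a claim that it is large would be unsupported.

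**The code may already do this.** The R code cited as an additional file is not among the documents, so the point concerns the SAP text only.

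**Conclusion.** The concern holds in limited form. For sodium, potassium, chloride, bicarbonate and BUN, and for highest, final and serial creatinine, the SAP text specifies no model containing the patient's own pre-enrollment value, although those values are collected. The cost is efficiency, at most 25% to 49% of outcome variance for an assumed ρ of 0.5 to 0.7, plus presenting-value differences that go uncorrected. It is not an inability to see modest effects.

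Correlation and SD are assumptions, and the gain shrinks if the listed covariates are in the model. Corrections for multiple testing declares the additional secondary analyses, which include the secondary-outcome comparisons, hypothesis-generating. This is a worthwhile refinement and does not threaten the trial's main conclusion.

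**What to change.** - **Electrolytes and BUN:** in the GEE or regression models, add the last pre-enrollment value of the same analyte, with a missing-value indicator. Where the named method is a rank-sum test, which takes no covariate, take the adjusted comparison from a regression.
- **Highest, final and serial creatinine:** add log study-baseline creatinine and an indicator for formula-estimated baselines.
- **Change to highest creatinine:** keep it as a listed outcome, but take its between-group estimate from the baseline-adjusted model.
- **Emergency department and operating-room patients:** use the last value before the first assigned crystalloid, since some receive assigned fluid before ICU admission (SAP, Study Interventions) and a later value could already reflect it.
- **If the R code already has a baseline term:** say so in the SAP text.

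The cost is SAP wording, a covariate and indicator per model, and patient-level derivation of the baseline time. No new data are needed for most patients: the laboratory values are extracted, and protocol 8.4.2, Fluid Administration, records the timing and location of fluid orders from 24 hours before ICU admission. The primary analysis does not change.
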